## Scan Session – Resting State

• During the resting state scan, participants will be asked to relax with eyes closed. During this time, participants will be instructed to empty their mind.

#### Scan Session – Emotional Faces Task

• Participants will be presented with stimuli consisting of either picture of faces in various emotional states (angry, fearful, sad, happy and neutral) or scrambled faces (control). In the emotion condition, participants have to indicate the gender of the face. In the control condition, participants have to press the corresponding button as indicated on the screen, *i.e.*, an arrow pointing left or right.

Scan Session – Traumatic Audio Script Cue Paradigm

• This task will closely replicate the imaginal exposure technique, which is a characteristic feature of trauma-focused psychotherapy. A neutral and a traumatic event will be collected during preparatory session and condensed into audio recording of approximately 30 seconds. During the scanning session, each participant will be instructed to lie still, breathe through his/her nose, and allow himself/herself to begin focusing on the neutral script as soon as the script is played. As soon as the participant has heard the script, he/she is encouraged to remember all sensations that are associated with the event for 60 seconds. The neutral script will be followed by the traumatic condition. The procedure will be as follows:

60 sec Rest

30 sec Neutral script > 60 sec time to remember all sensations > 120 sec break

30 sec Neutral script > 60 sec time to remember all sensations > 120 sec break

60 sec SUDS-neutral script

30 sec Traumatic script > 60 sec time to remember all sensations > 120 sec break

30 sec Traumatic script > 60 sec remember all sensations

60 sec SUDS-traumatic script

Scan Session – Subjective Units of Distress Scale (SUDS)

- Participants will be asked to rate how distressed they feel after preparation of neutral and traumatic script at preparatory session 3.
- Participants will be asked to rate how distressed they feel at set times throughout the scan session as explained in Table 1 above: Schedule of Procedures for MRI Session.

## 5.0 Sub-Study Objectives and Evaluation

The primary objective of this sub-study will be to explore possible biological correlates of treatment outcomes obtained from MDMA-assisted psychotherapy among participants with PTSD.

- To investigate pre-post effects of MDMA-assisted psychotherapy on brain function and connectivity as measured by functional magnetic resonance imaging (fMRI), including response to trauma-unrelated emotional stimuli (emotional faces), response to trauma symptom provocation (personal trauma narrative). The outcome variables will be compared between timepoints (Baseline scan V 4.1 and post-treatment scan V 14.1).
- To examine the relationship between fMRI outcome variables and the primary outcome variable, namely change in CAPS-5 Total Severity Score from Baseline (Visit 3) to 13 weeks post Baseline (Visit 14).

## 6.0 Methods, Data Analysis, and Hypothesis

All measures will be performed on a 3-Tesla MRI machine (Siemens or Philips, depending on site) equipped with a standard head coil. The measurements will remain the same for both scan 1 (pretreatment) and scan 2 (posttreatment). The impact of MDMA-assisted psychotherapy (scan 2) on the outcome measures will be compared with those at baseline (scan 1).

fMRI sub-study data may be analyzed at the later stage and presented in an addendum to the clinical study report.

## 7.0 Resting State

During resting state, participants will be instructed to relax with eyes closed. During this time, they will be instructed to empty their mind.

## 8.0 Data analysis: Resting State

Resting state images will be analyzed via functional connectivity. Functional connectivity data will be produced with the MATLAB toolbox DPARSF. Sphere regions of interest (ROI) will be created that are located in key areas of the fear circuitry system. Average time courses will be obtained for each sphere ROI and correlational analysis will be performed voxel wise to generate FC maps for each sphere ROI. Finally, the correlation coefficient map will be converted into z-maps by Fisher's r-to-z transform to improve normality.

## 9.0 Hypothesis: Resting State

We hypothesize that upon completion of the treatment (post-treatment scan vs. baseline scan), there will be decreased BOLD activity in the amygdala and hippocampus. Additionally, there will be decreased coupling between the vmPFC and hippocampus and increased coupling between the amygdala and hippocampus, and that these changes will positively correlate with subjective effects ratings of the MDMA experience.

#### **10.0 Emotional Faces Task**

The experimental paradigm during functional MRI scanning consists of a blocked design, including an emotion condition with angry, fearful, sad, happy and neutral face stimuli known to reliably activate the anterior medial temporal lobe including the amygdala [128], and a control condition with scrambled faces. Twenty-four stimuli were selected for each of five facial expressions, comprising 12 female and 12 male faces. Each face will not be presented more than four times. The control condition (scrambled faces) will be presented 80 times. To reduce anticipatory effects, an event-related design was used that involved a pseudo-random presentation of a total of 200 stimuli against a black background. Each photograph will be shown on the screen for 2.5 s, with an interstimulus (black screen) interval varying between 0.5 and 1.5 s. Participants have to indicate each face's gender by pressing one of two buttons with the index finger of the left or right hand on two magnet-compatible button boxes. During the presentation of scrambled faces, participants have to press left or right buttons in conformity with the instruction presented on the screen (*i.e.*, an arrow pointing to the left or to the right). The reaction time will be recorded.

## 11.0 Data Analysis: Emotional Face-Matching Task

Image analysis will be performed with SPM12 (http://www.fil.ion.ucl.ac.uk/spm). The first five EPI-volumes will be discarded, and the remaining images will be realigned to the first volume. Images will be then co-registered to the anatomical scan, corrected for differences in slice acquisition time, spatially normalized to the MNI T1 template, resampled into  $2 \times 2 \times 2$  mm^3 voxels, and spatially smoothed (8 mm FWHM). Statistical analysis will be performed within the framework of the general linear model. To assess the influence of MDMA-assisted psychotherapy on neural responsivity, the two experimental conditions (posttreatment scan; baseline scan) will be modeled as box-car regressors convolved with the canonical hemodynamic response function of SPM12. In addition, the realignment parameters will be included to

model potential movement artifacts, as well as a constant. Furthermore, a high-pass filter (cut-off 1/128 Hz) will be included, and temporal autocorrelation will be modeled with an AR (1) process. Contrast images subtracting the visuo-motor control condition from the emotion condition will be obtained and analyzed in subsequent random effects models.

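### The face-task fMRI model in Appendix A 11.0 names the two scans, not the stimulus types, as its regressors, so the planned contrasts cannot be formed from it

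*Protocol*

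**What the plan says.** Appendix A, 11.0 gives the first-level model for the face task. The task regressors are defined in one sentence: "the two experimental conditions (posttreatment scan; baseline scan) will be modeled as box-car regressors convolved with the canonical hemodynamic response function". Realignment parameters are added, "as well as a constant", then "a high-pass filter (cut-off 1/128 Hz) will be included", with AR(1) errors. The paragraph closes: "Contrast images subtracting the visuo-motor control condition from the emotion condition will be obtained and analyzed in subsequent random effects models".

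Appendix A, 10.0 describes the task. Faces with five expressions and a scrambled-face control are mixed within one run: "an event-related design was used that involved a pseudo-random presentation of a total of 200 stimuli". The opening sentence of the same section calls the design blocked.

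Appendix A, 12.0 states the hypothesis: after treatment, a smaller amygdala response to fearful versus angry faces. Appendix A, 5.0 makes the pre-post change in such fMRI outcomes, and its relation to CAPS-5 change, the sub-study's objectives. The SAP (2.0 Introduction) says that a separate SAP for the sub-study is to be prepared; it is not among the documents.

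**The concern.** A first-level contrast is a weighted sum of the coefficients of modelled conditions. Section 11.0 names two conditions, the post-treatment scan and the baseline scan, and then takes a contrast between two others, emotion and control, which it has not modelled. The scan is the factor to compare at the second level, between a participant's two contrast images. It has been put where the stimulus types belong.

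At stake is the face-task outcome, one of the fMRI outcomes that 5.0 names. An analyst who follows 11.0 literally gets no estimate of the evoked response to faces. An analyst who departs from it must choose the regressors, the event or block structure and the contrast without a written rule, possibly after seeing data.

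**Working it through.** **Inputs from the documents**
- 10.0: 24 stimuli for each of 5 expressions, 80 scrambled faces, 200 in total; each shown for 2.5 s, with a gap of 0.5 to 1.5 s.
- 4.1, Table 1 (MRI schedule): 12 minutes for the face task.
- 11.0: constant, high-pass cut-off 128 s, first five volumes discarded.

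**Assumed, because not stated:** repetition time (TR) 1, 2 or 3 s; 0 or 5 of the dropped volumes fall within the task; gaps uniform on 0.5 to 1.5 s; one random event order per case; a double-gamma approximation to the canonical response function.

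**Step 1. Reproduce the plan's figures.** Stimuli: 24 × 5 + 80 = 200, as stated. Run length: 200 × (2.5 + 1.0) s = 700 s = 11.7 min, against 12 min stated. The gap limits give 200 × 3.0 = 600 s (10.0 min) to 200 × 4.0 = 800 s (13.3 min).

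**Step 2. What is left of a whole-scan box-car, each scan as its own session.** Let x be the convolved box-car and Z the constant plus the filter's cosine terms. Their number is the whole part of 2 × 700/128 = 10.9, so 10. The share of x left to estimate its coefficient is the sum of squares of x after regression on Z, divided by the sum of squares of x.

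| TR (s) | Task volumes dropped | Left after constant | Left after constant and filter |
|---|---|---|---|
| 1 | 0 | 0.69% | 0.60% |
| 1 | 5 | 0.077% | 0.077% |
| 2 | 0 | 0.76% | 0.66% |
| 2 | 5 | 0.018% | 0.012% |
| 3 | 0 | 0.83% | 0.71% |
| 3 | 5 | 0.007% | 0.005% |

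The remainder comes essentially from the onset ramp of the response function. It says nothing about faces.

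**Step 3. Both scans concatenated with one constant.** The two convolved box-cars correlate at -0.984 to -0.9999. Their difference is in effect a single step with a period of about 2 × 700 = 1,400 s, far slower than 128 s. The filter leaves about 1.9% of it.

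**Step 4. Can the stated contrast be formed?** Neither scan regressor changes when the stimulus changes from face to scrambled image. In the layout of step 2, the filtered box-car explains at most 1.3% of the filtered emotion-minus-control time course. No weighting of the two scan coefficients equals emotion minus control, and fearful versus angry needs a finer split still. Realignment parameters and AR(1) errors add no stimulus coding.

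**Step 5. The same check with stimulus regressors.** With emotion (120 events) and control (80 events) entered separately within a scan, 88% to 95% of each regressor's variance about its mean survives the constant and the filter. The design has 2 + 1 + 10 = 13 columns and rank 13. Emotion minus control has a standard error of 0.15 to 0.28 residual standard deviations (before allowing for autocorrelation). With six stimulus types there are 6 + 1 + 10 = 17 columns, and the same construction again gives full rank.

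**The case against.** The strongest reply is that this is a drafting slip. The last sentence of 11.0 can be carried out only with emotion and control regressors, so they were probably intended, and a competent analyst would notice at once. The detail may also belong in the fMRI SAP, and 6.0 of the appendix allows the data to be analysed later and reported in an addendum. The point about intent stands, and it limits the finding to a mis-specified description. It does not remove it: no section of either document names the stimulus regressors, and a SAP still to be prepared is not evidence that it will.

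Two stronger readings are tempting, and the documents do not support either.
- A reader might infer that the model is rank-deficient and cannot be fitted at all. That is true only of unconvolved box-cars. Section 11.0 convolves them, and the onset ramp then makes the columns formally independent: rank 3 of 3 with one constant, 4 of 4 with a constant per scan. The coefficients exist but carry almost no usable information.
- A reader might infer that the sub-study will compare mean signal between scans, and might put a figure on the power lost. The documents plan no such test. They also give no sub-study sample size, fMRI effect size, between-session signal variation or repetition time from which to compute power.

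**Conclusion.** Section 11.0 is wrong as written. The named regressors are nearly collinear with the constant. With each scan as its own session, under 1% of their sum of squares survives the constant and the filter; with concatenated scans, about 1.9% of their difference survives. These sizes rest on the 700 s run derived from 10.0 and on the assumed repetition times of 1 to 3 s. The main conclusion needs no such assumption: the regressors do not code stimulus type, so they cannot yield emotion minus control or fearful versus angry. The two labels for the design in 10.0 add to the ambiguity.

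The consequence stays within an optional, exploratory sub-study run at selected sites. The CAPS-5 primary, SDS secondary and safety analyses are unaffected. The text should be corrected before the face-task data are analysed.

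**What to change.** In Appendix A 11.0, and in the fMRI SAP to be prepared:
1. Replace the two scan regressors with one convolved regressor per stimulus type (angry, fearful, sad, happy, neutral, scrambled) within each scan, with a separate constant for each scan.
2. For each participant and scan, form two named contrasts: emotion minus control, and fearful minus angry.
3. Compare post-treatment with baseline in a paired random-effects model of those contrasts.

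In 10.0, reconcile the two labels for the design. The pseudo-random 2.5 s presentation described there is event-related. If blocks were meant, the presentation rule has to change, and the regressors must still be by stimulus type. State also that stimulus order and onset times are kept for each scan; 10.0 mentions only reaction times.

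The cost is wording in an appendix and a section of a SAP not yet prepared. No new scans or participants are needed, and the analysis remains within the software already named.

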## 12.0 Hypothesis: Emotional Face-Matching Task

We hypothesize that upon completion of the treatment (post-treatment scan vs. baseline scan) participants will display a reduced amygdala response to fearful vs. angry faces.

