# 1.2.3 MDMA-Assisted Psychotherapy for PTSD

Many psychotherapies for PTSD involve the induction and extinction of abnormal autonomic responses through revisiting traumatic experiences in psychotherapy with an appropriate level of emotional engagement [20]. To be effective, exposure must be accompanied by a degree of emotional engagement or "fear activation" while avoiding dissociation or overwhelming emotion [37]. This has been referred to as working within the "optimal arousal zone" or "window of tolerance" [38-40].

The combined neurobiological effects of MDMA increase compassion for self and others, reduce defenses and fear of emotional injury, and enhance communication and introspection. MDMA produces anxiolytic and prosocial effects, which counteract avoidance and hyperarousal in the context of therapy. PTSD increases amygdala activity, causing heightened encoding of fearful memories and decreases blood flow in the prefrontal cortex. In contrast, MDMA acutely decreases activity in the amygdala [41], and there is some indication that MDMA may increase activity in the prefrontal cortex (PFC) [42]. Another study showed increased functional connectivity between the amygdala and hippocampus, and decreased connectivity between the amygdala and PFC [43]. Brain imaging after MDMA indicates less reactivity to angry facial expressions and greater reward in happy faces [41], compatible with its reported reduction in fear or defensiveness, and counteracts the stimulation of the amygdala observed in animal models of conditioned fear, a state similar to PTSD [44-46]. The reduction in stress-induced activation of the amygdala may be supported and enhanced by interacting with the therapy team during and after the MDMA experience. The subjective effects of MDMA create a productive psychological state that enhances the therapeutic process. MDMA enhances perceived self-authenticity [47] and a naturalistic study suggests that it can increase self-compassion [48], effects that may support and contribute to the therapeutic process. MDMA is capable of inducing unique psychopharmacological effects, including decreased fear and increased wellbeing, sociability, interpersonal trust, acceptance of self and others, and ability to address these issues without extreme disorientation or ego loss due to alert state of consciousness. These factors taken together can provide the opportunity for a corrective emotional experience.

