The neurocircuitry model of PTSD hypothesizes that the amygdala, medial prefrontal cortex (mPFC) and hippocampus are dysfunctional [131]. Specifically, the amygdala is hyperactive in response to threat-related stimuli [127], and this accords with both an exaggerated fear response and overgeneralized fear conditioning [131]. Additionally, compared to traumatized controls, people with PTSD show a relative failure to activate the mPFC (hypoactivation) when engaged in trauma imagery [127] and the mPFC fails to exert top-down control over the amygdala [131], leading to both emotional dysregulation and impaired fear extinction. Lastly, impaired hippocampal activity may underlie deficits in recognizing present contexts as safe during fear extinction [131].

Combat veterans with PTSD show more physiological reactivity, including increased heart rate and blood pressure in response to combat related stimuli than combat veterans without PTSD [132]. Neuroimaging studies have demonstrated that the amygdala is hyperactive when personalized trauma scripts are used [133, 134]. Increased amygdala activation also extends to emotional, non-trauma related stimuli. Exposure to emotional faces has been an especially effective probe of amygdala function [135]. There is increased amygdala activity in individuals with PTSD in response to fearful versus happy faces [125, 130, 136, 137] and this increased amygdala activation has been positively correlated with PTSD symptom severity [121, 138]. Successful exposure therapy has been associated with decreased amygdala activation during fear conditioning [139].

The insula is structurally interconnected with the amygdala and specifically sensitive to salient environmental stimuli, marking such stimuli for further processing [140]. Several studies have reported hyperactivity of the insula in PTSD using trauma script symptom provocation [141, 142] as well as increased activity when processing fearful versus happy facial expressions [143]). A positive correlation has been reported between insula activation and PTSD severity [121] as well as in other anxiety disorders [135, 144, 145].

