directed activity [161]. Alterations in the resting state functional connectivity (RSFC) of the default mode network have been discovered for individuals with PTSD and may be associated with disturbances in self-referential processing and dissociative symptoms [157]. Individuals with PTSD have been found to have increased positive RSFC between the amygdala and insula [162] and reduced positive connectivity between the amygdala and hippocampus. Additionally, there are negative correlations between the amygdala and the mPFC, rACC and dorsal ACC, supporting the hypothesis of an inhibitory role of the mPFC in relation to the amygdala.

In the first resting state fMRI investigation of MDMA in healthy participants, the intensity of the euphoric effect correlated with reductions of cerebral blood flow (CBF) in the amygdala and hippocampus. Amygdalar response to angry faces was reduced in people given MDMA [163]. Moreover, a decreased RSFC was found between the hippocampus and vmPFC, whilst an increased RSFC was seen between the hippocampus and amygdala. The magnitude of the former correlated with the intensity and euphoria of the MDMA experience, suggesting that MDMA may exert some of its therapeutic effect by decreasing the coupling between the mPFC and hippocampus [54].

MDMA administration in healthy participants has been shown to produce changes in regional blood flow, including increases in ventromedial frontal and occipital cortex, inferior temporal lobe and cerebellum; and decreases in the motor and somatosensory cortex, temporal lobe including left amygdala, cingulate cortex, insula and thalamus [42]. This has the potential to reverse some of those abnormalities seen in participants with PTSD.

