A recent study showed that participants given MDMA are more likely to use words relating to friendship, support and intimacy, in comparison to the drug methamphetamine, which by contrast reduced participants' discussions about compassion [163]. MDMA appears to enhance the quality of social interactions and thereby improve relationships, recently tested using a simulated experimental paradigm of social exclusion by Frye et al, 2014, showing how participants taking MDMA exhibited reduced social exclusion phenomena [164]. Another recent study showed similarly that MDMA enhances levels of shared empathy and pro-social behavior compared with placebo [165]. Furthermore, Wardle showed how MDMA can facilitate a faster detection of happy faces, and reduces the detection of negative facial expressions, which leads participants to view their social interaction partner as more caring [166]. Additionally, a recent study by comparing MDMA against intranasal oxytocin demonstrated the former produced the greater improvements in prosocial communication [167]. And the positive effects of MDMA appear consistent across different environments, with participants examined in San Francisco, Chicago and Basel demonstrating broadly similar pro-social outcomes [167].

Emotional numbing is a characteristic feature of PTSD, where sufferers find it difficult to benefit from the positive effects of social contact (DSM-5). There is a strong link between the strength of the therapeutic alliance and positive outcome in PTSD therapy [168]. MDMA induces the release of oxytocin and produces robust pro-social feelings, the strength of which is strongly correlated to the level of oxytocin released [169].

Oxytocin has been found to markedly dampen fear related amygdala activity, causing a decreased stress response, decreased social anxiety [170-172] and alters negative evaluations of aversive conditioned stimuli such as fearful faces [173]. The amygdala is required for accurate social judgements of others based on their facial expression [174]. Healthy volunteers given MDMA were better able to detect positive facial expressions than negative ones [165]. As described above, the vmPFC plays an inhibitory role opposing the amygdala and is essential for fear extinction learning. MDMA causes increased vmPFC activation and decreased amygdala activation when given to healthy controls [42] and in response to observing angry faces [163].

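### The face-task hypothesis (fearful vs. angry) matches neither its rationale nor the contrast planned in Appendix A 11.0, and it can cancel or reverse if both threat responses fall

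*Protocol*

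**What the plan says.** **Hypothesis.** Appendix A 12.0 states that, comparing the post-treatment scan with baseline, "participants will display a reduced amygdala response to fearful vs. angry faces".

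**Analysis.** Appendix A 11.0 says that "the two experimental conditions (posttreatment scan; baseline scan) will be modeled as box-car regressors", and then: "Contrast images subtracting the visuo-motor control condition from the emotion condition will be obtained and analyzed in subsequent random effects models". By 10.0, the emotion condition pools angry, fearful, sad, happy and neutral faces, and the control is scrambled faces. Section 11.0 lists no regressor for a single expression and no fearful-versus-angry contrast.

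**Rationale.** Appendix A 1.0 states the PTSD abnormality this way: "There is increased amygdala activity in individuals with PTSD in response to fearful versus happy faces". The same section uses fearful versus happy for the insula and for the rostral anterior cingulate and medial prefrontal findings. On MDMA it says "Amygdalar response to angry faces was reduced in people given MDMA", and later reports "decreased amygdala activation when given to healthy controls [42] and in response to observing angry faces". Protocol 1.2.3 adds: "Brain imaging after MDMA indicates less reactivity to angry facial expressions and greater reward in happy faces".

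**Aim.** Appendix A 5.0 and the end of 1.0 ask about the response to emotional faces, and to stressful or threatening stimuli, in general. SAP 2.0 says that a separate fMRI SAP will be written.

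**The concern.** Fearful and angry faces are both threat expressions. A hypothesis about fearful relative to angry is a difference of two changes. Its null is that the two responses change by the same amount, which is not the same as no change in the response to threat. The one expression for which the protocol cites an MDMA effect stands on the side being subtracted.

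If the fMRI SAP carries 12.0 forward literally, a general fall in the amygdala response to threat could appear as no effect on the stated hypothesis, or as an effect in the wrong direction. That matters beyond the face task: Appendix A 1.0 says that brain changes may further support efficacy conclusions, and 5.0 plans to relate the fMRI outcomes to the change in CAPS-5.

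**Working it through.** **The plan's own figures.** The stimulus counts in Appendix A 10.0 agree: 24 × 5 + 80 = 200, the stated total. At 2.5 s per picture plus a mid-range interval of 1.0 s, 200 × 3.5 s = 700 s, or 11.7 minutes, against the 12-minute slot in Appendix A 4.1. No sample size, alpha, SD or effect size is given for this hypothesis, so there is no power figure to reproduce.

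**Contrasts.** Let dF, dA, dS, dH and dN be the post-minus-baseline amygdala changes for fearful, angry, sad, happy and neutral faces.

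- Hypothesis in 12.0: dF − dA
- Contrast used in the rationale: dF − dH
- Contrast in 11.0: (dF + dA + dS + dH + dN)/5 minus the change for scrambled faces

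The table assumes no change for sad, happy, neutral or scrambled faces. Units are SDs.

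| Assumed scenario | dF | dA | Fearful − angry | Fearful − happy | All emotions − scrambled |
|---|---|---|---|---|---|
| Equal fall | −0.5 | −0.5 | 0.00 | −0.50 | −0.20 |
| Angry falls more | −0.3 | −0.5 | +0.20 | −0.30 | −0.16 |
| Angry only | 0 | −0.5 | +0.50 | 0.00 | −0.10 |
| Fearful falls more | −0.5 | −0.3 | −0.20 | −0.50 | −0.16 |
| Fearful only | −0.5 | 0 | −0.50 | −0.50 | −0.10 |

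The 12.0 contrast cancels in the first row, has the wrong sign in the next two, is attenuated in the fourth and is intact only in the last. The 11.0 contrast never changes sign. In the first row it keeps (0.5 + 0.5)/5 = 0.20 of a 0.50 fall, which is 2/5.

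**Illustrative power.** For a paired test at two-sided 0.05, with the SD of each contrast's change set to 1, the probability of a significant fall is Φ(−1.96 − d√n). Under the equal fall:

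- Fearful − angry: d = 0, so Φ(−1.96) = 2.5% at any n.
- Fearful − happy: d = −0.5. At n = 20, Φ(−1.96 + 0.5 × √20) = Φ(0.276) = 61%. At n = 10 and n = 40 it is 35% and 89%.
- All emotions − scrambled: d = −0.2, giving 9%, 14% and 24% at n = 10, 20 and 40. Averaging over expressions may reduce the SD below 1, so these could be low.

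If only angry falls, fearful − angry is significant in the wrong direction with probability Φ(0.5 × √20 − 1.96) = 61% at n = 20. If fearful falls somewhat more (fourth row), its power is 14% at n = 20.

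**Choice of reference.** Fearful versus happy is not safe alone. If only angry falls it is 0.00. If happy rises by an assumed 0.5 and nothing else changes, it is 0 − 0.5 = −0.50 without any change in threat response.

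**The case against.** The strongest objection is that 11.0 does not plan the fearful-versus-angry test. Its contrast pools all emotions against scrambled faces, so under the assumptions above a general fall in threat response would still show with the right sign. This stands, and it limits the harm to the stated hypothesis. It does not remove the mismatch: that contrast does not test 12.0, and it is diluted if only the two threat responses change.

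Second, no sentence says that fearful and angry responses fall together, let alone equally. The angry-face evidence comes from people given MDMA (healthy controls, where stated), whereas Appendix A 3.0 places the second scan about 8 weeks after the last Experimental Session. The therapy evidence in Appendix A 1.0, closer to a pre-post design, concerns fear conditioning and fear processing. A fear-specific prediction is therefore arguable. This also stands: cancellation is a possibility, not a forecast. Yet the protocol does not argue for fear specificity, and an authored specificity hypothesis would need its own contrast in 11.0.

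Third, the fMRI SAP may settle the point. It is not among the documents, and a SAP faithful to 12.0 would inherit the problem.

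**Conclusion.** The point holds as one of consistency and choice of contrast. The hypothesis in 12.0 departs from the fearful-versus-happy comparison used throughout its rationale, and 11.0 provides no test of it.

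A reader might infer more: that the protocol expects both threat responses to fall together, so that the effect will cancel and the sub-study will miss or reverse a real change. The documents do not support this. Cancellation needs equal falls and reversal needs a larger fall for angry faces; neither is stated. The one contrast that 11.0 specifies would do neither in the scenarios examined.

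The algebra does not depend on sample size. The 2.5% and 61% figures do rest on assumptions: a 0.5 SD fall in both threat expressions, no change for happy faces, unit SD for each contrast and, for the second figure, N = 20. They illustrate the mechanism and do not measure this study's risk. Only an exploratory, optional sub-study is affected.

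**What to change.** In Appendix A 12.0, state the hypothesis as a reduced amygdala response to fearful versus happy faces, post-treatment scan against baseline, with a parallel angry versus happy contrast. Add fearful and angry each against neutral or scrambled faces as a check, because Protocol 1.2.3 reports a changed response to happy faces under MDMA (as reward, not as an amygdala result). Keep fearful versus angry, if wanted, as a secondary specificity contrast.

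In 11.0 and the fMRI SAP, model each expression as its own regressor within each scan and name the same contrasts. Rewording 12.0 alone would leave the new hypothesis without a specified test.

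The cost is wording and analysis time. All five expressions and the scrambled faces are already shown, so no new stimuli, scans or participants are needed. The downside is a few more contrasts to report, each resting on 24 stimuli per expression rather than the pooled 120.
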